Clinical Study Protocol				
1. Title and Phase of Study				
Title: Study regarding the clinical efficacy of Synatura® in patients with chronic bronchitis type COPD				
Phase: Interventional, single center, single group, open-label study				
2. Name and Address of Study Site				
Site Name: The Catholic University of Korea Seoul St. Mary's Hospital				
Address: [name]				
3. Name and Title of Principal Investigator, Subinvestigator and co-investigator				
Role	Name	Affiliation	Title	Contact (Mobile)
Principal Investigator	[name]	Pulmonology and Allergy	Associate Professor	[name]
4. Name and Title of Clinical Research Pharmacist				
Not applicable: the study drug (Synatura®) is currently approved by Korean Ministry of Food and Drug Safety (MFDS) and prescribed for patients with chronic bronchitis, and this is an open-label study with no placebo.				
5. Name and Address of Sponsor				
Ahngook Pharm([name])				
6. Background and objectives of Study				

Synatura® is a drug commonly used to suppress cough and sputum in patients with acute upper respiratory tract infection and chronic inflammatory bronchitis. According to the Phase III studies conducted in Korea, the safety and efficacy of Synatura® on antitussive and expectorant effects were confirmed in patients with acute upper respiratory infection and chronic inflammatory bronchitis. However, no studies have been conducted for the effects of Synatura® in patients with COPD. COPD is divided into emphysema type and chronic bronchitis type, while typical clinical symptoms of chronic bronchitis are cough and sputum. Therefore, Synatura®, which is effective for chronic bronchitis, is expected to be effective in patients with chronic bronchitis accompanied by COPD.
 
 Primary Objective: Establish clinical efficacy of Synatura® in patients with chronic bronchitis-type chronic obstructive pulmonary disease
				


4) Pregnant women
 
5) Breast-feeding women
 
6) Patients with fructose intolerance
 
Sample size: 30 subjects
 
Rationale:
 
The primary outcome of this study is CAT reduction after taking Synatura®.
 
The margin of error was set at 3 points. Also, the standard deviation of the CAT score is reported to be 7.7 from the previous study (Int J Chron Obstruct Pulmon Dis. 2015;10:1623-1631). Assuming Alpha to be 0.05, beta 0.2, 25.307 subjects will be calculated. Assuming a drop rate of 0.15, 29.773 subjects will be required.

10. Study Period

From approval date of the study to 31 December 2018

11. Clinical Study Methods (including Dose, Treatment Method, Treatment Period and Concomitant Medications)

1) Overview
 
The clinical study on the effect of Synatura® will be conducted in COPD patients with symptoms of chronic bronchitis. The enrolled patients will be prescribed Synatura® following measurement of pre-dose pulmonary functions, quality of life and systemic inflammatory state. Pulmonary functions, quality of life and systemic inflammatory state will be repeatedly measured after taking Synatura® for 3 months, and the changes from pre-dose measurements will be observed.
 
2) Group: Single group
 
3) Study drug: Synatura® 15 mL TID for 3 months
 
Patients will be administered the above drug, and changes from pre-dose measurements will be observed.
 
① Changes from pre-dose measurement in pulmonary functions will be observed (FVC, FEV1, post bronchodilator FVC, FEV1).
 
② Changes from pre-dose scores in quality of life will be observed (COPD assessment test - CAT).
 
③ Changes from pre-dose measurement in systemic inflammatory state will be observed (CRP, fibrinogen, IL-6, TNF-a).

Item	At enrollment	After 3 months
Pulmonary functions	O	O
CAT	O	.O
BSS	O	O
CRP	O	.O
fibrinogen	O	.O
IL-6	O	.O
TNF-a	O	O

4) Prohibited concomitant medications

Xanthine derivatives (aminophylline, theophylline, choline theophyllinate, oxtriphylline), central nervous system stimulants (cocaine, amphetamine, codeine), antitussives and expectorants except for the study drug

5) Cost for procedures

In the case of pulmonary function test performed before and after treatment, it will be prescribed as a non-covered item and the actual cost of the test is paid the subject back.

6) Transportation cost

Patients participating in the study will be paid 50,000 KRW per visit.

7) Cost for study drug

Synatura® will be prescribed for 3 months, and patients will receive the drug at the pharmacy in the study site. The cost for study drug will be paid from the research fund as a non-covered drug.

12. Observation Items/Clinical Test Items, Observation and Test Methods

1) Pulmonary functions - pulmonary function test will be performed before and 3 months after taking Synatura®.

2) Quality of life - CAT score and BSS will be performed before and 3 months after taking Synatura®.

3) Systemic Inflammation - blood samples will be taken before and 3 months after taking Synatura®, then stored and measured by ELISA in the laboratory.

13. Expected Side Effects and Precautions

According to the results of previous phase III studies, nausea, vomiting and dizziness can occur after taking Synatura®. Most of them are mild side effects and severe side effects that require medical interventions are not expected to occur. Currently, Synatura® is approved by the Ministry of Food and Drug Safety in March 2011, and widely used in clinical practice. In the 4-year post-marketing survey conducted in 606 patients for re-examination in Korea, the incidence of adverse events was reported to be 2.64% (16/606 patients, 16 cases) regardless of the causal relationship. No significant adverse events have been reported.

14. Discontinuation/Withdrawal Criteria
If the patient no longer wants to participate in the study
15. Evaluation Criteria, Evaluation Methods and Analysis Methods for Efficacy (Statistical Analysis Method)
The paired t-test will be used to establish the statistical significance of changes pre-dose measurement. 1) Changes from pre-dose measurement in pulmonary functions will be observed (FVC, FEV1, post bronchodilator FVC, FEV1). 2) Changes from pre-dose scores in quality of life will be observed (COPD assessment test - CAT). 3) Changes from pre-dose measurement in systemic inflammatory state will be observed (CRP, fibrinogen, IL-6, TNF-a).
16. Evaluation Criteria, Evaluation Methods and Reporting Methods for Safety (including Side Effects)
Side effects evaluation criteria and evaluation methods - in the investigator's opinion, severity based on CTCAE 4.0, relationship to study drug and actions will be determined. Reporting adverse events Suspected unexpected serious adverse reactions will be reported to IRBs immediately. Suspected unexpected serious adverse reactions will be reported within following timeframe: ① Causes death or be life-threatening: within 7 days ② For other suspected unexpected serious adverse reactions: within 15 days.
17. Agreement on Compensation for Victims
1) For the safe characteristics of Synatura®, which will be administered in this study, it is considered that the risk to a victim is extremely low. 2) Any serious adverse events or unexpected problems should be reported to IRBs immediately (within 24 hours). 3) In case of damage due to participation in the study, study staffs will be notified and patients will be received urgent emergency treatment by staffs from Department of Pulmonology and Allergy. It will also be reimbursed under the responsibility of the principal investigator for all medical problems that arise. 4) Insured for compensation.
18. Care and Treatment Criteria for subjects after the Study
After the end of the study, patients may continue to take Synatura® or discontinue. After the end of the

study, continuation of taking Synatura® will be decided by the investigator based on the patient's symptoms (cough and sputum).

19. Measures to Protect the Safety of Subjects

- 1) Voluntary consent will be obtained from the subject based on sufficient explanation and understanding of the study.
- 2) Personal identification number (resident registration number, case number, name) of the subject will not be collected.
- 3) Extracted information will be safely stored for 5 years to prevent leakage, and discarded completely.
- 4) After extracting the data, the patient ID will be used after substituting with an alternative key. Access to the file will be limited to the person in charge of the study conduct and analysis

20. Other Necessary Details for safe and scientific implementation of Study

In case of damage due to participation in the study, study staffs will be notified and patients will be received urgent emergency treatment by staffs from Department of Pulmonology and Allergy.

Attachments: Informed Consent Form, Case Report Form Two references

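### The Section 6 objective claims established efficacy, but one open-label group tested before and after treatment can show only that mean CAT changed

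*Protocol*

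**What the plan says.** Section 6 of the protocol gives the aim: "Primary Objective: Establish clinical efficacy of Synatura® in patients with chronic bronchitis-type chronic obstructive pulmonary disease". The same section says of the existing evidence: "However, no studies have been conducted for the effects of Synatura® in patients with COPD".

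Section 1 describes the design as "Interventional, single center, single group, open-label study", and Section 4 adds that "this is an open-label study with no placebo". The sample size rationale names the endpoint: "The primary outcome of this study is CAT reduction after taking Synatura". Sections 11 and 12 schedule CAT at two times only, enrollment and 3 months. Section 15 gives one method for efficacy, a paired t-test of change from pre-dose.

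The wording of Section 11 is more modest: "the changes from pre-dose measurements will be observed". Section 15 likewise speaks of observing changes.

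On size, the rationale says "The margin of error was set at 3 points" and "the standard deviation of the CAT score is reported to be 7.7 from the previous study". It then states alpha 0.05, beta 0.2, 25.307 subjects, and 29.773 after a drop rate of 0.15.

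**The concern.** The objective is a statement about cause: the drug works in this population. The planned test addresses something narrower, namely whether mean CAT at 3 months differs from mean CAT before dosing. In one unblinded group the observed change is the drug effect plus whatever would have happened anyway. The second part includes regression to the mean, the expectation of patients who know they are treated, and other care. Two measurements per patient in one group cannot separate the two parts.

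The text available gives no control group, historical reference, performance threshold or expected untreated change that would bridge this gap. By the protocol's own account this would be the first study of the product in COPD. As the objective is worded, a significant fall in CAT would be open to being read as efficacy established.

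The problem runs both ways. If CAT would worsen without the drug, the test is conservative and a real effect may be missed.

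**Working it through.** **1. What the sample size targets.** Inputs from the rationale: SD 7.7, margin 3 points, alpha 0.05, drop rate 0.15.

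- n = (1.95996 × 7.7 / 3)² = 25.307
- 25.307 / 0.85 = 29.773, rounded up to 30

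Both stated figures reproduce. This is the formula for a two-sided 95% CI with a half-width of 3 points around one mean. The stated beta of 0.2 does not enter, and nothing in it compares treated with untreated patients. The study is sized to estimate a mean.

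**2. What the test's error rate covers.** Let b be the mean fall in CAT that would occur with an inert product under the same conditions. The null of the paired t-test is zero mean change. It coincides with zero drug effect only when b = 0. If b > 0, an inert product is declared significant too often; if b < 0, too seldom.

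**3. How sensitive the result is to b.** Setting: 26 completers (25.307 rounded up), two-sided 0.05, critical t = 2.060 on 25 df, noncentrality b / (SD of change / √26), counting significant falls only.

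The protocol gives neither b nor the SD of the change. For the SD, a pre/post correlation r was assumed, with the same SD of 7.7 at both times: SD of change = 7.7 × √(2(1 − r)).

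- r = 0.8: 7.7 × √0.4 = 4.87
- r = 0.5: 7.7 × √1 = 7.7
- r = 0.3: 7.7 × √1.4 = 9.11

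Chance of a significant fall with an inert product:

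| Untreated fall b (points) | SD 4.87 | SD 7.7 | SD 9.11 |
|---|---|---|---|
| 0 | 2.5% | 2.5% | 2.5% |
| 0.5 | 7.3% | 5.0% | 4.5% |
| 1 | 17% | 9.3% | 7.8% |
| 2 | 52% | 25% | 19% |
| 3 | 86% | 48% | 36% |

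A simulation of 200,000 trials at SD 7.7 gave 2.5%, 5.0%, 9.2%, 24.6% and 48.1% for the same five values of b.

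**4. The other direction (SD 7.7).** An untreated rise of 1 or 2 points lowers the inert-product rate to 0.5% or 0.06%. A true 3-point drug effect then nets a fall of 3 − 1 = 2 or 3 − 2 = 1 points. The chance that it shows as a significant fall drops from 48% to 25% or 9%.

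**5. Precision of the mean change.** The t-based 95% half-width is 2.060 × SD / √26:

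- SD 7.7: 3.11 points
- SD 4.87: 1.97 points
- SD 9.11: 3.68 points

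All 30 patients completing would give 2.88, 1.82 and 3.40. The protocol's 3-point margin describes the change only if 7.7 is the SD of the change, whereas the rationale calls it the SD of the score.

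**The case against.** The strongest reply is that nothing is hidden. The protocol says several times that there is one open-label group, and Sections 11 and 15 speak only of observing changes. No decision rule equates p < 0.05 with efficacy. Lack of a comparator is a limit of every single-arm study, so what remains is one verb in a short protocol. This is largely right. It is why the point is confined to the Section 6 objective and leaves the design alone. But the objective is what a study is read against, and here it promises what the rest of the document does not.

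Second, Section 6 cites Phase III evidence of efficacy in acute upper respiratory infection and chronic inflammatory bronchitis, and Section 11 excludes other antitussives and expectorants. The first is the protocol's ground for expecting an effect in COPD, but an expectation is not a comparator. The second limits one competing explanation and leaves the others. If a patient stopped such a drug at entry, that could itself move CAT.

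Third, the text between the Section 6 objective and the fourth exclusion criterion is not available. It might qualify the objective or require clinical stability at entry, which could lessen regression to the mean. It cannot supply a control group in a study declared to have one group.

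Fourth, the percentages rest on assumed drifts and correlations. That stands: they show sensitivity, not likelihood.

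Finally, the title also speaks of clinical efficacy. It presents a study regarding efficacy and does not claim to establish it.

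**Conclusion.** The point holds and should be corrected. The stated objective needs a property that the design lacks, and no choice of analysis for two time points in one unblinded group can provide it. This conclusion rests on the protocol's own description and on the null of the paired t-test, not on any assumed figure.

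The size is unknown, because the protocol gives no basis for the untreated change. Over the assumed SDs, an untreated improvement of 1 point would raise the false-claim rate from 2.5% to between 7.8% and 17%, and one of 2 points to between 19% and 52%. An untreated worsening would instead hide a real effect. Confidence is medium, because part of the text is not available and all the sizes are assumed.

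**What to change.** Keep the design, the sample size and all tests, and make two changes of wording.

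- **Section 6:** *Primary objective: to estimate the change in CAT score over 3 months of Synatura treatment in patients with chronic bronchitis-type COPD.*
- **Section 15, add:** *The primary result is the mean change in CAT score from pre-dose to 3 months with its 95% CI; as there is no control group, a statistically significant change will not be reported as established efficacy.*

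The title and Section 11 need no change. The team should expect a half-width slightly above the planned 3 points at 26 completers if the SD of the change is 7.7, and wider or narrower as the true SD of the change dictates.

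The cost is a more modest headline claim. No patients, visits or procedures are added, and no test is removed.

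### Minor: the 3-point margin of error rests on a normal quantile, but under the planned paired t-test 25–26 pairs give about 3.1–3.2 points if 7.7 is the SD of the change

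*Protocol*

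**What the plan says.** The Rationale under the sample-size heading ("Sample size: 30 subjects") names the endpoint, "The primary outcome of this study is CAT reduction after taking Synatura", and then gives its inputs: "The margin of error was set at 3 points" and "the standard deviation of the CAT score is reported to be 7.7 from the previous study". From these it concludes "Assuming Alpha to be 0.05, beta 0.2, 25.307 subjects will be calculated" and "Assuming a drop rate of 0.15, 29.773 subjects will be required". It names neither the formula nor whether alpha is one- or two-sided.

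The analysis is fixed in Section 15: "The paired t-test will be used to establish the statistical significance of changes pre-dose measurement".

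**The concern.** The sample size and the analysis use different reference distributions. The calculated number treats the SD as known, while the paired t-test estimates it from roughly 25 differences and pays for that with a larger quantile (2.064 on 24 df, 2.060 on 25 df, against 1.960). The stated number of subjects therefore does not quite deliver the stated margin under the stated test.

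CAT change is the primary outcome, and the Rationale is the only justification given for 30 subjects. The 3 points is also the only precision figure in the protocol. A reader who later compares the observed confidence interval or p-value with that figure would find the study slightly less precise than promised, even if every planning assumption held.

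**Working it through.** **Inputs.** From the Rationale: margin 3 points, SD 7.7, alpha 0.05, beta 0.2, dropout 0.15, 30 enrolled. From Section 15: paired t-test.

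**Reproducing the plan's figures.** For a confidence interval around one mean, n = (z × SD / margin)².

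- With z = 1.95996: (1.95996 × 7.7 / 3)² = 25.307, as stated. The rounded 1.96 gives 25.308.
- Dropout: 25.307 / 0.85 = 29.773, as stated.
- Other formulas do not reproduce it. A one-sided z gives 17.8. A paired power calculation at 80% gives 51.7 two-sided or 40.7 one-sided.

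So 25.307 is a two-sided 95% precision figure, and beta does not enter it.

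**Pairs available.** 30 × 0.85 = 25.5, so 25 or 26.

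**Half-width under the paired t-test.** Half-width = t(0.975, n−1) × SD / √n. The p-value for an observed fall of 3.0 uses t = 3√n / SD. Both take the SD of the differences as 7.7.

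| Pairs | Normal half-width | t half-width | t for a 3.0 fall | Two-sided p |
|---|---|---|---|---|
| 25 | 3.02 | 3.18 | 1.948 | 0.063 |
| 26 | 2.96 | 3.11 | 1.987 | 0.058 |
| 27 | 2.90 | 3.05 | 2.024 | 0.053 |
| 28 | 2.85 | 2.99 | 2.062 | 0.049 |
| 30 | 2.76 | 2.88 | 2.134 | 0.041 |

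For example, at 25 pairs: 2.064 × 7.7 / 5 = 3.18. Relative to 3 points this is 3.18 / 3 = 1.06, and at 26 pairs 3.11 / 3 = 1.04. The half-width first falls to 3 or less at 28 pairs, which at 15% dropout means 28 / 0.85 = 32.9, or 33 enrolled.

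**Sensitivity to the SD.** The Rationale gives 7.7 as the SD of the score, not of the within-patient change. With equal SDs before and after and correlation r, the SD of change is 7.7 × √(2(1 − r)), which equals 7.7 only at r = 0.5. The documents give no r. Over an assumed range at 25 pairs:

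- r = 0.3: SD of change 9.11, half-width 3.76.
- r = 0.7: SD of change 5.96, half-width 2.46.

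Whatever the SD, the t-based half-width at 25–26 pairs is about 5% wider than the normal one (3.178 / 3.018 = 1.05).

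**Power, for context.** For a true 3-point fall and SD 7.7, the paired t-test has 46% power at 25 pairs and 48% at 26. Power of 80% would need about 54 pairs (54 / 0.85 = 63.5, or 64 enrolled).

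**The case against.** **This is an approximation, not an arithmetic error.** That stands. The figures follow correctly from the stated inputs, a normal quantile is a common planning shortcut, and the gap is only 0.11–0.18 CAT points. What remains is that the protocol itself fixes both the margin and the test, and at this sample size the two do not match.

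**The uncertainty about the SD is much larger.** This also stands: half-widths of 2.46 to 3.76 over the assumed correlations dwarf the quantile effect. It is a reason to state the SD assumption openly, not to leave the margin at 3.

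**A reader might infer that a 3-point fall cannot be significant in this trial.** The documents do not support that.

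- The p of about 0.06 needs a sample SD near 7.7. A 3.0 fall is significant at 25 pairs if the sample SD is below 3 × 5 / 2.064 = 7.27, and at 26 pairs if it is below 7.43.
- It is also significant at SD 7.7 if 28 or more patients complete.
- At 25 pairs even a z-test gives p = 0.051, because 25 is below 25.307, so the t quantile is not the whole reason.
- Two-sidedness is inferred from 25.307. A one-sided p would be about 0.03.

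**A reader might also take 3 points as the planned effect or the detectable limit.** The Rationale calls it only a margin of error, so missing significance at 3 points contradicts no stated target.

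**The unused beta is the larger defect in the same Rationale.** Agreed. Correcting the quantile alone would leave an implied 80% power that the number does not provide, so the two need to be handled in one edit.

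**Conclusion.** The point holds as a minor one. The 25.307 (29.773 after dropout) is a normal-quantile precision figure, and the planned paired t-test on 25–26 pairs gives a two-sided 95% half-width of 3.18 or 3.11 points rather than 3. At a sample SD of 7.7, an observed 3-point fall would sit just on the non-significant side at those numbers and on the significant side from 28 pairs upward.

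This rests on three assumptions: that 7.7 is the SD of the change, as the protocol's formula implicitly takes it; that the test is two-sided at 5%, as 25.307 implies; and that dropout is the planned 15%. It does not show that 30 subjects is miscalculated on its own inputs, or that the trial must enrol 33.

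**What to change.** Keep the planned 30 subjects and restate the Rationale as a precision statement, for instance: *With 25–26 evaluable pairs, and assuming the SD of the CAT change is 7.7, the 95% margin of error from the paired t-test is about 3.1–3.2 points.* Remove the implication that 25.307 subjects give 3 points under the planned analysis.

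In the same edit, say that this figure does not use the stated beta of 0.2, so that 30 is not read as a number chosen for 80% power.

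The cost is a sentence or two in the Rationale. No patients are added and the test does not change. The downside is a slightly less favourable stated margin.

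### The sample size for a within-patient CAT change uses the SD of the CAT score, with no SD of change or correlation stated, so 25.307 and 29.773 are unsupported in an unknown direction

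*Protocol*

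**What the plan says.** The Rationale under the sample size heading of the protocol names the outcome: "The primary outcome of this study is CAT reduction after taking Synatura". It then gives the inputs and results in order:

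- the target: "The margin of error was set at 3 points";
- the spread: "the standard deviation of the CAT score is reported to be 7.7 from the previous study";
- the result: "Assuming Alpha to be 0.05, beta 0.2, 25.307 subjects will be calculated";
- the allowance for dropout: "Assuming a drop rate of 0.15, 29.773 subjects will be required".

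The number enrolled is 30. Section 11 describes a single group, and section 12 has CAT measured twice, before treatment and 3 months later. Section 15 gives the analysis: "The paired t-test will be used to establish the statistical significance of changes pre-dose measurement".

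The protocol states no SD for the CAT change and no correlation between the two readings. Nothing in it says that 7.7 refers to a change.

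**The concern.** A paired t-test works on one number per patient, the difference between the two readings. Its standard error, and the width of the matching confidence interval, depend on the SD of those differences. The SD of a score describes how far patients differ from one another. The two SDs are linked through the correlation between a patient's readings, and either can be the larger.

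The Rationale puts a score SD where the SD of change belongs. This is the only justification given for the size of the study. If the SD of change differs from 7.7, the completers calculated will not deliver the stated 3 points: the interval will be wider or narrower, and the protocol gives no means of telling which.

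**Working it through.** **Inputs from the protocol.** Margin E = 3 points, SD = 7.7 (described as that of the score), alpha = 0.05, dropout 0.15, 30 enrolled (all from the sample size Rationale). Paired analysis (section 15), two readings (section 12).

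**Step 1: reproduce the protocol's figures.** The formula that fits is the two-sided 95% half-width for one mean:

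- n = (1.96 × SD / E)² = (1.96 × 7.7 / 3)² = 25.307.
- After dropout: 25.307 / 0.85 = 29.773, hence 30.

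Both figures reproduce, so 7.7 was entered as the SD of the quantity analysed.

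**Step 2: the SD of change.** Assume the SD is 7.7 at both visits and let r be the correlation between them:

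- SD(change) = 7.7 × √(2(1 − r)).

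This equals 7.7 when 2(1 − r) = 1, that is at r = 0.5. The protocol gives no r, so the values below are assumptions chosen to show the range.

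**Step 3: completers needed by the protocol's own formula, and precision expected.** Column 3 is (1.96 × SD(change) / 3)². Column 4 is 1.96 × SD(change) / √25.307, the protocol's own method. Column 5 uses the t distribution with 25 completers (30 × 0.85 = 25.5): t(0.975, 24) × SD(change) / 5, with t = 2.064.

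| Assumed r | SD(change) | Completers for 3 points | Half-width, z, n = 25.307 | Half-width, t, n = 25 |
|---|---|---|---|---|
| 0.3 | 9.1 | 35.4 | 3.55 | 3.8 |
| 0.5 | 7.7 | 25.3 | 3.00 | 3.2 |
| 0.7 | 6.0 | 15.2 | 2.32 | 2.5 |
| 0.8 | 4.9 | 10.1 | 1.90 | 2.0 |

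At r = 0.5 the last two columns differ (3.0 against 3.2) because of the t distribution and the rounding down to 25, not because of the SD. The effect of the SD is read down a column.

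**Step 4: how firm is the break-even at 0.5?** If the 3-month SD is k × 7.7, the variance of the change is 7.7² × (1 + k² − 2kr), which equals 7.7² when r = k/2. So k = 0.8 moves the break-even to r = 0.4, and k = 1.2 moves it to r = 0.6.

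**The case against.** The best defence is that a score SD is a workable stand-in, and a cautious one whenever a patient's two readings correlate above about 0.5. In that case the interval is narrower than 3 points and the plan delivers more than it promises. This stands as far as it goes. The protocol, however, neither makes the argument nor states a correlation. At r = 0.3 its own formula needs 35.4 completers, more than all 30 patients enrolled.

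A second defence is that the 7.7 in the cited study may in fact be an SD of change. That source is not available here, so the point cannot be settled. What is certain is that the protocol describes 7.7 as belonging to the score.

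A reader might be tempted by several stronger readings, which the document does not support:

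- *Thirty patients are too few.* This follows only if the correlation is low, and the protocol gives no reason to expect that.
- *The figures hold only at a correlation of exactly 0.5.* This needs equal SDs at both visits (step 4), and above the break-even the 3-point margin is still met.
- *The margin itself comes from 7.7.* It was chosen, so only 25.307 and 29.773 depend on the SD.
- *Low power shows the size of this fault.* The 25.307 makes no use of the quoted beta of 0.2, so power would fall short even if 7.7 were the right SD of change. That is a separate fault in the same sentence.
- *A non-significant result could not be interpreted.* The paired t-test and its interval use the SD observed in the trial, so the result can be read whatever SD was planned.

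**Conclusion.** Wrong as written. The Rationale sizes a within-patient change with an SD that it attributes to the score, so 25.307 and 29.773 are not supported for the primary outcome. The multiplication and division are correct; the fault lies in the input, and any other sample size formula fed with 7.7 would inherit it.

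Over assumed correlations of 0.3 to 0.8, the completers needed for a 3-point half-width range from 35.4 down to 10.1. The direction of the error is unknown: the margin is missed below about r = 0.5 and met above it. These figures rest on three assumptions: an SD of 7.7 at both visits, correlations that the document does not supply, and the protocol's own description of what 7.7 measures.

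**What to change.** Keep the 30 patients and rewrite the Rationale paragraph.

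- Replace the score SD with the SD of the 3-month within-patient CAT change, give its source, and recompute 25.307 and 29.773.
- If only a score SD can be found, say so, state the assumed correlation and the assumption of equal SDs, and show the range.
- In place of the single 3-point figure, state the precision expected. For example: about 25 completers give a t-based 95% confidence interval half-width for the mean CAT change of about 3.8 points if the correlation is 0.3, 3.2 if 0.5, 2.5 if 0.7 and 2.0 if 0.8.

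The cost is one reworded paragraph, with no added patients and no change of design. The drawback is that a single margin becomes a range whose upper end looks less favourable than 3 points. Holding to 3 points at a correlation of 0.3 would instead mean enrolling 35.4 / 0.85 = 41.7, so 42 patients; keeping 30 means accepting the range. This rewording does not settle the unused beta, which needs its own correction.

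### The 25.307 subjects come from a confidence-interval width formula with no beta in it, so the sample size rationale does not support the type II error of 0.2 that it states

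*Protocol*

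**What the plan says.** The rationale comes under the heading "Sample size: 30 subjects", just before Section 10 of the protocol. It names the endpoint ("The primary outcome of this study is CAT reduction after taking Synatura") and then gives two inputs: "The margin of error was set at 3 points" and "the standard deviation of the CAT score is reported to be 7.7 from the previous study". From these it concludes "Assuming Alpha to be 0.05, beta 0.2, 25.307 subjects will be calculated", and then "Assuming a drop rate of 0.15, 29.773 subjects will be required".

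The design is described in Section 1 as "Interventional, single center, single group, open-label study". Section 15 names the analysis: "The paired t-test will be used to establish the statistical significance of changes pre-dose measurement". No other test is named, and no other justification for 30 subjects is given.

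The protocol states no expected mean CAT change, no SD of the within-patient change, no correlation between the two visits, and no sidedness for alpha.

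**The concern.** Beta 0.2 means 80% power. Since the only test in the protocol is the paired t-test, a reader will take the rationale to say that this test has 80% power for the primary CAT comparison.

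The inputs are not those of a power calculation. A margin of error is the half-width of an interval; it is not an effect to be detected. The SD of a score at one time is also not, in general, the SD of the change between two times, and the latter is what the paired t-test needs.

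If beta was not used, the protocol claims an error rate that its calculation does not control. A non-significant CAT result could then be read as evidence of no effect, on the strength of a 20% type II error that was never built in.

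**Working it through.** **Inputs, all from the sample size rationale:** margin 3 points; SD 7.7; alpha 0.05; beta 0.2; dropout 0.15. The paired t-test is from Section 15.

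**1. Reproducing the protocol's figures.** The precision formula is n = (z₀.₉₇₅ × SD / E)².

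- (1.95996 × 7.7 / 3)² = 25.307, the stated figure to three decimals.
- 25.307 / (1 − 0.15) = 29.773, also exact.

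Neither step contains beta.

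**2. The same inputs with beta 0.2.** Read 3 points as the target change and 7.7 as the SD of the paired change, with n = ((z_α + z₀.₈₀) × SD / 3)².

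| Alpha 0.05 | Normal formula | Completers, normal | Completers, paired t |
|---|---|---|---|
| Two-sided | ((1.95996 + 0.84162) × 7.7 / 3)² = 51.71 | 52 | 54 |
| One-sided | ((1.64485 + 0.84162) × 7.7 / 3)² = 40.73 | 41 | 43 |

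None is near 25.307. Two-sided, 52 to 54 completers would mean 62 to 64 enrolled after dividing by 0.85.

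**3. Why the gap is a factor of two.** If the half-width equals the change to be detected, then 3 × √n / SD = 1.96. Normal-approximation power is Φ(1.96 − 1.96) = Φ(0) = 50%, ignoring the negligible opposite tail. So the formula used corresponds to a beta of about 0.5 for a true change of 3 points, whatever SD is put in, provided that SD is the SD of the change.

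**4. What 30 enrolled gives if the SD of change is 7.7.** At 15% dropout, 30 × 0.85 = 25.5 completers. The values below use the t and noncentral t distributions, two-sided 0.05 except where marked.

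| Completers | Power for 3 points | Power, one-sided 0.05 | Change detectable with 80% power | 95% CI half-width |
|---|---|---|---|---|
| 25 | 46% | 60% | 4.50 | 3.18 |
| 26 | 48% | 61% | 4.40 | 3.11 |
| 30 | 54% | 67% | 4.08 | 2.88 |

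**5. If 7.7 is the SD at each visit.** Assuming equal SDs at both visits, the SD of change is 7.7 × √(2(1 − r)), where r is the correlation between visits. The protocol gives no r, so the values below are assumptions.

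| Assumed r | SD of change | Two-sided power for 3 points, 25 completers | Completers for 80% power (t) |
|---|---|---|---|
| 0.3 | 9.1 | 35% | 75 |
| 0.5 | 7.7 | 46% | 54 |
| 0.6 | 6.9 | 55% | 44 |
| 0.7 | 6.0 | 67% | 33 |
| 0.8 | 4.9 | 84% | 23 |

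**6. What would be needed for 80% power for 3 points.** The SD of change must be at most 5.14 with 25 completers, 5.25 with 26 and 5.67 with 30. With a per-visit SD of 7.7, 25 completers need r of at least 1 − 5.137² / (2 × 7.7²) = 0.78. If all 30 complete, r must be at least 0.73.

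**The case against.** The strongest defence is that the rationale speaks openly of a margin of error, and both printed numbers are correct for that purpose. On this view the sample size was always precision-based, and beta 0.2 is a stray label. The protocol never writes out 80% power, and the rationale does not name the paired t-test. This stands as a description of how the number arose. It does not rescue the sentence, which presents beta 0.2 as an assumption behind 25.307, while the planned analysis is a significance test of an efficacy objective.

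A second defence is that underpowering has not been shown. This also stands. If the two CAT scores are strongly correlated, power could exceed 80%: at r = 0.8 it is 84% with 25 completers and 90% with 30. The protocol does not assume such a correlation, so the defence shows what might be true and not what was derived. The 46% figure should not be quoted as the trial's power.

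Third, alpha could be one-sided, since the outcome is a reduction. The 1.96 in the calculation points to two-sided. A one-sided test at SD of change 7.7 would still give only 60% to 67% power.

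Finally, a half-width of 3 is itself only approximate. With the t distribution it is slightly over 3 at 25 or 26 completers, and 28 are needed to bring it to 3 or less.

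**Conclusion.** The concern holds. The figure of 25.307 is a correct precision calculation presented as if it used beta 0.2. No one-sided or two-sided formula that uses beta 0.2 on the stated inputs gives it; the two-sided requirement is about double.

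That conclusion rests only on the protocol's own numbers. Any statement about actual power is conditional on the SD of the paired change: 46% to 54% two-sided for 25 to 30 completers if it is 7.7, and 35% to 84% at 25 completers over an assumed correlation of 0.3 to 0.8 if 7.7 is the per-visit SD. The protocol therefore states a type II error rate for its primary outcome without deriving it. This must be corrected, because the paragraph is the sole basis for the number of patients.

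**What to change.** Either of two changes to the sample size rationale would do.

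**(A) Present the size as precision-based.** Remove beta 0.2 as the basis of 25.307 and write, for example: *Thirty patients are enrolled so that about 25 to 26 complete. If the SD of the CAT change is 7.7, the 95% confidence interval for the mean change has a half-width of about 3.1 to 3.2 points. On the same condition, the two-sided 0.05 paired t-test has about 46 to 48% power for a true change of 3 points and 80% power for about 4.4 to 4.5 points. These figures change with the SD of change.* The text should add that 7.7 was reported for the CAT score and is used here as an assumption for the change.

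**(B) Present a power calculation.** State and justify an expected CAT change and an SD of the paired change, fix the sidedness of alpha, use a formula that contains beta, and report the power that 30 enrolled (25 to 26 completers) then gives. If that formula asks for more than 30, the text should report the power actually achieved and not claim 80%.

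Both are wording changes that can keep 30 patients and leave the endpoint and test alone. The cost of (A) is giving up the beta 0.2 statement for a conditional and, at an SD of change of 7.7, less favourable one. The cost of (B) is finding support for two inputs that the protocol does not now contain.
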